8.3.2 Application Site Reactions

The following application site reactions will be evaluated at each visit based on the scale provided below:

Signs and Symptoms:

Erythema

Pyoderma

STATISTICAL ANALYSIS PLAN

Ivermectin Lotion 0.5%

Protocol / Study No. 71691702

Excoriation
Pain
Pruritus
Edema

Grading Scale:

Absent	0	
Mild	1	(slight, barely perceptible)
Moderate	2	(distinct presence)
Severe	3	(marked, intense)

Application site reactions and ocular discomfort will be compared descriptively among treatment groups. A frequency summary table comparing the application site reactions for each treatment group will be presented by visit.

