8.0 INTRODUCTION

8.1 Disease Being Treated

Pediculus humanus capitis, the head louse, is an ectoparasite whose only host are humans. The louse feeds on blood several times daily and resides close to the scalp to maintain its body temperature.¹ Head lice infestation is widespread, affecting both children and adults. In the United States it is estimated that between 6 and 12 million infestations occur each year among children 3 to 11 years of age.² Head lice infestations can be asymptomatic, particularly with an initial infestation or when the infestation is mild. Itching is the most common symptom associated with head lice infestation and is caused by an allergic reaction to louse bites. Although head lice are not known to transmit any disease, untreated infections can lead to poor sleep and sores on the head caused by scratching. These sores can become infected with bacteria commonly found on a person's hands.^{3,4}

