10.5.2 Visit 2 (Day 2): Interim Visit

Visit 2 must occur the day after patient dosing. All treated household members will return for follow-up at Visit 2 only.

1. **Concomitant Medication:** Review the patient's use of any new or ongoing concomitant medications since the last visit.
2. **Adverse Events:** Patients will be questioned about any health status changes/AEs since last visit. All AEs will be recorded.
3. **Vital Signs:** The patient's vital signs will be recorded (pulse, blood pressure, temperature and respiration rate).
4. **Pregnancy Test:** A urine pregnancy test will be required of all female patients of childbearing potential.
5. **Louse Examination:** An Investigator or staff member, who is experienced and trained in detection and evaluation of head lice, will perform a visual inspection for the presence of live lice (i.e., live adults and/or nymphs). Louse examination should be conducted for 15 minutes or longer, unless any live lice are detected in less time. If any live lice are found during the exam, the patient should be discontinued and provided with alternative therapy. Duration of examination and number of live lice should be recorded in the patient's eCRF.
6. **Application Site Reactions:** Patients will be asked about any application site reactions since last visit (see Appendix A). Any reactions will be recorded.
7. **Ocular Irritation Assessment:** Patients will be questioned about any ocular discomfort resulting from contact with the study product. Any discomfort will be documented as an AE.
8. **Return Study Product:** Patients will return the used study product tube.
9. **Collect and Review Patient Diary:** Study staff will collect previously provided diary and review for compliance with the protocol.
10. **Provide Patient Diary:** A diary will be provided to record AEs and concomitant medications.

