10.6.7 Louse Examination

The Investigator or other qualified staff will perform a visual inspection for the presence of live lice (i.e., live adults and/or nymphs) at each visit. Louse examination should be conducted for 15 minutes or longer, unless any live lice are detected in less time. Duration of examination and number of live lice should be recorded in the patient's eCRF. Patients with live lice present at Visits 2 or 3 should be discontinued from the study and provided with alternative therapy.

Determination of live lice can be aided by the use of a mild magnification (e.g., 5x).

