10.6.9 Application Site Reactions

At Visit 1, the Investigator will grade the individual signs and symptoms (erythema, pyoderma, excoriation, pain, pruritus, edema) per Appendix A. This will serve as a baseline for subsequent assessments of application site reactions. At Visits 2, 3, and 4, application site reactions will be assessed by clinic staff. Reactions will be scored and recorded.

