Total AEs	Total AEs	xx (xx.x%)	xx (xx.x%)	xx (xx.x%)	xx (xx.x%)	xx (xx.x%)	xx (xx.x%)
Ear and labyrinth disorders	Ear pain	xx (xx.x%)	xx (xx.x%)	xx (xx.x%)	xx (xx.x%)	xx (xx.x%)	xx (xx.x%)
	Hypoacusis	xx (xx.x%)	xx (xx.x%)	xx (xx.x%)	xx (xx.x%)	xx (xx.x%)	xx (xx.x%)
	etc.						

etc.

N = Total number of events in each treatment group; Percentage is based on total number of events.

Test: Ivermectin Lotion, 0.5% (Actavis Laboratories UT, Inc.)

Reference: SKLICE® (ivermectin) Lotion, 0.5% (Arbor Pharmaceuticals, LLC)

Placebo: Placebo (vehicle) lotion (Actavis Laboratories UT, Inc.)

OUTPUT: L:\DEV\917\71691702\SAS\OUT\XXXX

Created on: ddmmmyy hh:mm

Page 1 of N

STATISTICAL ANALYSIS PLAN

Ivermectin Cream 0.5%

Protocol / Study No. 71691702

T16.1.9.13 Summary of Frequency of Serious Adverse Events (Safety Population)

Body System	MedDRA Term	Test # Events	Reference # Events	Placebo # Events
Injury, poisoning and procedural complications	Alcohol poisoning	xx	xx	xx

Test: Ivermectin Lotion, 0.5% (Actavis Laboratories UT, Inc.)

Reference: SKLICE® (ivermectin) Lotion, 0.5% (Arbor Pharmaceuticals, LLC)

Placebo: Placebo (vehicle) lotion (Actavis Laboratories UT, Inc.)

OUTPUT: L:\DEV\917\71691702\SAS\OUT\XXXX

Created on: ddmmmyy hh:mm

Page 1 of N

STATISTICAL ANALYSIS PLAN

Ivermectin Cream 0.5%

Protocol / Study No. 71691702

T16.1.9.14 Summary of Frequency of Application Site Reaction (Safety Population)

Signs and Symptoms	Visit	Statistic	Placebo (N = xxx)	Test (N = xxx)	Reference (N = xx)
Edema	Visit 1	Absent	xxx (x.x%)	xxx (x.x%)	xxx (x.x%)
		Mild	xxx (x.x%)	xxx (x.x%)	xxx (x.x%)
		Moderate	xxx (x.x%)	xxx (x.x%)	xxx (x.x%)
		Severe	xxx (x.x%)	xxx (x.x%)	xxx (x.x%)
Visit 2					
Visit 3					
Visit 4					
Erythema					
Excoriation					
Pain					
Pruritus					
Pyoderma					

Test: Ivermectin Lotion, 0.5% (Actavis Laboratories UT, Inc.)

Reference: SKLICE® (ivermectin) Lotion, 0.5% (Arbor Pharmaceuticals, LLC)

Placebo: Placebo (vehicle) lotion (Actavis Laboratories UT, Inc.)

OUTPUT: L:\DEV\917\71691702\SAS\OUT\XXXX

Created on: ddmmmyy hh:mm

Page 1 of N

STATISTICAL ANALYSIS PLAN**Ivermectin Cream 0.5%****Protocol / Study No. 71691702****T16.1.9.15 Summary of Vital Signs
(Safety Population)**

Vital Signs	Visit	Statistic	Test (N = xxx)	Reference (N = xxx)	Placebo (N = xxx)
Systolic Blood Pressure (mmHg)	Visit 1	n	xxx	xxx	xxx
		Mean \pm SD	xxx.x \pm xxx.x	xxx.x \pm xxx.x	xxx.x \pm xxx.x
		Median	xxx.x	xxx.x	xxx.x

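### Application site reactions are graded at baseline, but the only planned table gives frequencies by visit and never compares a patient's later grade with that patient's own baseline.

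*SAP*

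**What the plan says.** Protocol 10.5.1 and 10.6.9 have the Investigator grade erythema, pyoderma, excoriation, pain, pruritus and edema at Visit 1 on the 0 to 3 scale of Appendix A. The stated purpose in 10.6.9 is: "This will serve as a baseline for subsequent assessments of application site reactions".

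SAP 8.3.2 plans a descriptive comparison: "A frequency summary table comparing the application site reactions for each treatment group will be presented by visit". Shell T16.1.9.14 (Safety population) lays this out as absent, mild, moderate and severe at each of Visits 1 to 4, under one N per arm. Listing L16.2.7.2 shows each patient's grades at all visits.

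Three other parts of the protocol bear on how that table reads:
- Protocol 8.1: "Itching is the most common symptom associated with head lice infestation", and "untreated infections can lead to poor sleep and sores on the head caused by scratching".
- Protocol 10.6.7: "Patients with live lice present at Visits 2 or 3 should be discontinued from the study".
- Protocol 10.5.2, with the same instruction in 10.5.3 and 10.5.4: "Patients will be asked about any application site reactions since last visit". Protocol 10.6.9, by contrast, has clinic staff assess and score reactions at Visits 2 to 4.

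**The concern.** The baseline grade is collected so that later grades can be read against it, yet no planned table does so for individual patients. At least two of the six items, pruritus and excoriation, are also effects of the infestation by the protocol's own account. A patient who itched before dosing and still itches afterwards is counted exactly like a patient whose itching began with the product.

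After Visit 2 a second difficulty arises. Who is still attending depends on whether lice were cleared, and clearance is expected to differ between the active arms and Placebo. A by-visit frequency at Visit 3 or 4 therefore describes differently selected groups.

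At stake is the local-tolerability part of the third objective, the safety comparison across all three arms. T16.1.9.14 is the only planned summary of the graded reactions.

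**Working it through.** The documents give no figure for site reactions, so there is none to reproduce. The check has three parts. All rates in parts 1 and 2 are assumptions for illustration.

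**1. What by-visit frequencies say about new reactions.** Let b be the share of patients with a sign at Visit 1 and v the share with it at Visit 2, in the same patients. The share newly affected (present at Visit 2, absent at Visit 1) is known only to lie between max(0, v − b) and min(v, 1 − b).
- b = 50%, v = 50%: from 0% to 50%.
- b = 50%, v = 40%: from 0% to 40%.
- b = 70%, v = 60%: from 0% to 30%.
- b = 30%, v = 20%: from 0% to 20%.

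A cross-tabulation of the Visit 1 grade by the Visit 2 grade observes this share directly, and also shows worsening in patients who already had the sign.

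**2. What selective attendance can do after Visit 2.** Assume no product effect. Let pruritus be present in q0 = 20% of cleared and q1 = 60% of infested patients. Let the share discontinued for lice be dA = 20% on an active arm and dP = 70% on Placebo. As a simplification, treat everyone still attending as cleared and leave out early-termination records.
- All patients followed, (1 − d)·q0 + d·q1: active 0.8 × 20% + 0.2 × 60% = 28%; Placebo 0.3 × 20% + 0.7 × 60% = 48%. Difference −20 points.
- Attending patients, over those attending: 20% v 20%. Difference 0.
- Attending patients, over the arm's Safety N, (1 − d)·q0: active 0.8 × 20% = 16%; Placebo 0.3 × 20% = 6%. Difference +10 points.

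The general forms of the differences are (q1 − q0)(dA − dP), 0, and q0(dP − dA). With dA from 10% to 30%, dP from 50% to 85%, and q0/q1 of 20%/60% or 10%/50%, the first runs from −8 to −30 points and the third from +2 to +15. The same absence of product effect gives a negative, zero or positive contrast, depending on who is counted and over what.

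**3. What the documents settle about rows and denominators.**
- Visit 2: site reactions are assessed at the same visit as the first post-dose louse examination, so the discontinuation rule has removed nobody yet.
- Visit 3: patients dropped at Visit 2 are missing. Patients first found infested at Visit 3 can be included.
- Visit 4: Protocol 12.2.4 has the Visit 4 form completed for early terminators, and 10.3.4 asks for End of Study procedures. Listings L16.2.5 and L16.2.8.1 have a combined column for Visit 4 or discontinuation. The SAP does not say whether such records, made around Day 2 or Day 8 and possibly after alternative therapy, are counted in the Visit 4 row.
- Denominator: the general rule in SAP Section 8 computes categorical percentages on non-missing data, which points to patients assessed. Shell T16.1.9.14 shows only the arm's N, with no n per visit and no footnote. The demographic shells base percentages on N, while the vital-signs shell T16.1.9.15 has an n row. SAP 8.5 on missing data covers only demographic and baseline variables. The denominator for this table is therefore not settled.

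**The case against.** The strongest reply is that baseline is not ignored. T16.1.9.14 has Visit 1 rows by arm, the listing gives individual grades, and randomized concurrent arms allow a between-group comparison without change scores. SAP Section 9 says the shells need not reflect every aspect of the study, so a shift table could be added later. Worsening also has another route: Protocol 10.7.1 counts worsening of an existing event as treatment-emergent, 11.8 makes clinically significant worsening of lice signs an adverse event, and relatedness is tabulated.

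Much of this stands. A reader might infer that the SAP makes no use of the baseline; it does show it at group level, but no table uses it within patient. The adverse-event route should catch marked worsening, but for lice signs it depends on a judgement of clinical significance, so lesser changes in grade need not appear there.

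A reader might also infer that Visits 3 and 4 contain only lice-free patients who stayed in the study. The documents do not support that, because patients first found infested at Visit 3 can be in its row and early terminators complete the Visit 4 form. Nor can the Placebo Visit 4 row be put at 25 to 76 patients, as 126 × (1 − 0.80) and 126 × (1 − 0.40) would suggest. The allocation ratio is redacted, the 40% to 80% discontinuation is assumed, the table uses the Safety population including non-index patients, and discontinued patients may be in the row.

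Finally, scoring at every visit is already called for by Protocol 10.6.9 and Appendix A. What remains is a mismatch of wording with 10.5.2 to 10.5.4, not a missing assessment.

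**Conclusion.** The point holds in a limited form. The plan collects a baseline for six items and then offers no summary of how many patients had a new or worsened reaction after dosing. From the planned table that share is only bounded, as widely as 0% to 50% when an assumed 50% show a sign at both visits.

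The Visit 3 and 4 contrasts between active and Placebo are hard to interpret, because attendance depends on lice status and the handling of early-termination records and the denominator are not settled. The size of any distortion cannot be taken from the documents; the ranges above rest wholly on assumed rates.

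Visit 2, the day after the single application, is free of this selection. Test versus Reference is affected less if their clearance is similar. The comparison is descriptive and feeds neither the equivalence nor the superiority decision. It is worth correcting because the correction is cheap and serves a stated objective.

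**What to change.** In SAP 8.3.2 and T16.1.9.14:
- Add, for each of the six items, a shift table from Visit 1 grade to Visit 2 grade by arm. Make the number and percent newly present or worsened the headline figure, with patients assessed at both visits as denominator.
- Show n assessed at each visit and state the percentage denominator in a footnote.
- Present early-termination records separately or by actual study day, not merged into the Visit 4 row.
- Treat Visits 3 and 4, and any worst post-dose summary, as supportive, with a footnote that later attendance depends on lice status. A worst-grade headline would give retained patients more assessments than those dropped for lice, and so more chances to record worsening.

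In the protocol, reconcile 10.5.2 to 10.5.4 (patients asked) with 10.6.9 and Appendix A (reactions scored at each visit), so that baseline and later grades can be compared.

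The SAP change costs one added table and some footnotes and needs no new data item. It can be made at any time before unblinding. A revision of the protocol text would need IRB review under 12.2.3. The shift table will not by itself separate lice from product: persistent lice can worsen a sign, and clearance can mask a new reaction. It does give the count of new and worsened signs, at the visit where the arms are most comparable.

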8.3.3 Vital Signs

Vital signs will be recorded (pulse, blood pressure, temperature and respiration rate) at each visit.

Descriptive summaries (number of observations, mean, standard deviation, minimum, median and maximum) will be provided by treatment and visit.

All data will be listed by treatment and patient.

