10.3 Selection of Study Population

10.3.1 Inclusion Criteria

1. Signed Institutional Review Board (IRB)-approved ICF that meets all criteria of current FDA regulations. For patients who are considered minors in the state the study is being conducted (< 18 years in most states), the parent or legal guardian should sign the consent form and the child will be required to sign a patient “assent” form, as appropriate. Patient 11-17 years of age will read and sign an IRB-approved assent form and patients 6-10 years of age will provide verbal assent. Patients 6 months-5 years of age will be exempt from providing assent based on the child’s comprehension and cognitive skills.
2. The patient and/or the patient’s parent (legal guardian) is willing to apply the study product as directed, comply with study instructions and commit to all follow-up visits for the duration of the study.
3. Male or non-pregnant, non-lactating female, 6 months of age or older.
4. Females of childbearing potential must not be pregnant or lactating at Visit 1 (as confirmed by a negative urine pregnancy test with a sensitivity of less than 50 mIU/mL or equivalent units of human chorionic gonadotropin). Women of childbearing potential must agree to the use of a reliable method of contraception (e.g., total abstinence, intrauterine device, a double-barrier method, oral, transdermal, injected, or implanted non-hormonal or hormonal contraceptive) throughout the study. Female patients using hormonal contraceptives should have been on the same product/dosing regimen for at least 28 days before Visit 1 and should not change this regimen during the study. A sterile sexual partner is not considered an adequate form of birth control.
5. Index patients (i.e., the youngest household member) must have an active head lice infestation, defined as ≥ 3 live lice (i.e., live adults and/or nymphs), at Visit 1.
6. Household members participating in the study must have at least one live louse (i.e., live adults and/or nymphs) at Visit 1.
7. All members of the household must be present for examination. Any male head of household who is unable to attend Visit 1 may be assessed by a second household member as being lice free.

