10.7.7 Recording and Reporting of Adverse Events

In this study, safety will be assessed by qualified study personnel by evaluating reported AEs, application site reactions, ocular safety assessment, vital signs measurements and use of concomitant medication.

For AE recording, the study period is defined for each patient as that time period from signature of the ICF through the end of the study (including any follow-up period).

All AEs that occur during the defined study period must be recorded on the source documentation, regardless of the severity of the event or judged relationship to the study product. For SAEs, the SAE form must also be completed and the SAE must be reported immediately (see section 10.7.8). The Investigator does not need to actively monitor subjects for AEs once the study has ended. However, SAEs occurring in a patient after the treatment of that patient has ended should be reported to the Sponsor if the Investigator becomes aware of them.

At each contact with the patient, the Investigator or designee must question the patient about AEs by asking an open ended question such as, "Have you had any unusual symptoms or medical problems since the last visit? If yes, please describe." All reported or observed signs and symptoms will be recorded individually, except when considered manifestations of a medical condition or disease state. A precise diagnosis will be recorded whenever possible. When such a diagnosis is made, all related signs, symptoms, and any test findings may be recorded collectively as a single diagnosis on the eCRF and, if it is an SAE, on the Serious Adverse Event Form.

The onset and end dates and times, action taken regarding study product, treatment administered, and outcome for each AE must be recorded on the source documentation.

The relationship of each AE to study product treatment and study procedures, and the severity and seriousness of each AE, as judged by the Investigator, must be recorded as described above.

The clinical course of each AE will be monitored at suitable intervals until resolved or stabilized or returned to baseline, until the patient is referred for continued care to a health care professional or until a determination of a cause unrelated to the study product or study procedure is made.

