Treatment group	Patient Number	Body System/ MedDRA Term/ AE Term	TX Area	Start /End Date	Severity	Relationship to Study Drug	Outcome	Action Taken with Study Drug/ Other Action Taken	SAE?
Test	xxx-xxx-xx	Nervous system disorders/ headache/ Headache	No	yyyy-mm-dd / yyyy-mm-dd	Mild	Not Related	Recovered	Drug withdrawn/ None	No

Reference

Placebo

Test: Ivermectin Lotion, 0.5% (Actavis Laboratories UT, Inc.)

Reference: SKLICE® (ivermectin) Lotion, 0.5% (Arbor Pharmaceuticals, LLC)

Placebo: Placebo (vehicle) lotion (Actavis Laboratories UT, Inc.)

OUTPUT: L:\DEV\917\71691702\SAS\OUT\XXXX

Created on: ddmmmyy hh:mm

Page 1 of N

STATISTICAL ANALYSIS PLAN

Ivermectin Cream 0.5%

Protocol / Study No. 71691702

L16.2.7.2 Listing of Application Site Reactions

Treatment Group	Patient Number	Visit	Edema	Erythema	Excoriation	Pain	Pruritus	Pyoderma
Test	xxx-xxx-xx	Visit 1	0	0	0	1	0	0
		Visit 2	0	1	0	0	0	0
		Visit 3	0	0	0	1	0	0
		Visit 4	0	0	0	1	0	0

Reference

Placebo

Test: Ivermectin Lotion, 0.5% (Actavis Laboratories UT, Inc.)

Reference: SKLICE® (ivermectin) Lotion, 0.5% (Arbor Pharmaceuticals, LLC)

Placebo: Placebo (vehicle) lotion (Actavis Laboratories UT, Inc.)

OUTPUT: L:\DEV\917\71691702\SAS\OUT\XXXX

Created on: ddmmmyy hh:mm

Page 1 of N

STATISTICAL ANALYSIS PLAN

Ivermectin Cream 0.5%

Protocol / Study No. 71691702

L16.2.8.1 Listing of Pregnancy Test Results

Treatment Group	Patient Number	Visit 1	Visit 2	Visit 3	Visit 4 or Discontinuation
Test	xxx-xxx-xx	Negative	Negative	Negative	Negative

Reference

Placebo

Test: Ivermectin Lotion, 0.5% (Actavis Laboratories UT, Inc.)

Reference: SKLICE® (ivermectin) Lotion, 0.5% (Arbor Pharmaceuticals, LLC)

Placebo: Placebo (vehicle) lotion (Actavis Laboratories UT, Inc.)

OUTPUT: L:\DEV\917\71691702\SAS\OUT\XXXX

Created on: ddmmmyy hh:mm

Page 1 of N

STATISTICAL ANALYSIS PLAN

Ivermectin Cream 0.5%

Protocol / Study No. 71691702

L16.2.8.2 Listing of Vital Signs

Treatment Group	Patient Number	Visit	Systolic BP (mmHg)	Diastolic BP (mmHg)	Pulse Rate (beats/min)	Respiration Rate (breaths/min)	Temperature (F)
Test	xxx-xxx-xx	Visit 1	120	70	84	18	98.6
		Visit 2	140	80	74	18	97
		Visit 3	120	70	84	18	98.6
		Visit 4	140	80	74	18	97

Reference

Placebo

Test: Ivermectin Lotion, 0.5% (Actavis Laboratories UT, Inc.)

Reference: SKLICE® (ivermectin) Lotion, 0.5% (Arbor Pharmaceuticals, LLC)

Placebo: Placebo (vehicle) lotion (Actavis Laboratories UT, Inc.)

OUTPUT: L:\DEV\917\71691702\SAS\OUT\XXXX

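### Vital signs are tabulated only as raw all-ages values by visit; the pre-dose Visit 1 value is never used for within-patient change, so the table is less sensitive than the data allow

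*SAP*

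**What the plan says.** Protocol 10.7.7 includes vital signs among the measures by which safety is assessed: "application site reactions, ocular safety assessment, vital signs measurements and use of concomitant medication". Protocol 10.5.1 to 10.5.4 record pulse, blood pressure, temperature and respiration rate at all four visits. The product is dispensed at Visit 1 and applied at home afterwards, so the Visit 1 value is pre-dose. Visit 2 is the day after dosing.

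The age range is wide, with no upper limit: "Male or non-pregnant, non-lactating female, 6 months of age or older" (Protocol 10.3.1).

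For analysis, SAP 8.3.3 says "Descriptive summaries (number of observations, mean, standard deviation, minimum, median and maximum) will be provided by treatment and visit" and then "All data will be listed by treatment and patient". The shell "T16.1.9.15 Summary of Vital Signs" shows n, mean with SD, median and range of the recorded value for each arm at each visit, in the Safety population. The shell "L16.2.8.2 Listing of Vital Signs" shows raw values by patient and visit, without age. Protocol 11.8 adds no vital-sign analysis. Neither document plans a change from baseline or an age breakdown for these measures.

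**The concern.** Normal pulse, respiration rate and blood pressure differ between infants, children and adults. In a pooled table the SD and range therefore partly reflect age. A shift of a few beats per minute after dosing is judged against that spread, and a value unusual for an adult can sit inside a range set by small children. Each patient has a pre-dose value that would remove most of the between-patient variation, and the plan does not use it.

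The third objective is to compare the safety of the three products, and vital signs are a named part of that assessment. At stake is the sensitivity of one descriptive safety table. No equivalence or superiority conclusion depends on it.

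**Working it through.** The plan states no figure for this analysis, so there is nothing to reproduce. Every SD, correlation, age gap and exit rate below is an assumption for illustration.

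**1. How pooling ages widens the SD.** Take two age groups in equal shares (m = 0.5), a within-age pulse SD of 12 beats/min and a gap between group means of 20, 35 or 50.

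All-ages SD = √(12² + m(1 − m) × gap²)

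- Gap 20: √(144 + 100) = 15.6
- Gap 35: √(144 + 306.25) = 21.2
- Gap 50: √(144 + 625) = 27.7

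**2. Raw value against change.** For n patients per arm, SD s and within-patient correlation r:

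- SE of an arm difference, raw values = s√(2/n)
- SE of an arm difference, change from Visit 1 = s√(2(1 − r)) × √(2/n)
- Ratio of the second to the first = √(2(1 − r)), which contains neither n nor s

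| r | Ratio | Fall in SE |
|---|---|---|
| 0.5 | 1.00 | none |
| 0.6 | 0.89 | 11% |
| 0.7 | 0.77 | 23% |
| 0.8 | 0.63 | 37% |
| 0.9 | 0.45 | 55% |

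Below r = 0.5 change would be noisier than the raw value, which is one reason to keep both.

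Is 0.8 reasonable under step 1? With a within-age correlation of 0.7 and an age gap that is stable over the two weeks, the SD of change is 12√(2 × 0.3) = 9.3, or 86.4 as a variance. The implied all-ages correlation is 1 − 86.4/(2 × all-ages variance). This gives 0.82, 0.90 and 0.94 for gaps of 20, 35 and 50.

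**3. In beats per minute, with s = 20 and r = 0.8.** If the 378 index patients split equally (the ratio is redacted), each arm has 126. The table uses the whole Safety population. With an assumed 0.5 to 1 non-index patient per index patient, that is 189 to 252 per arm.

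- n = 126: SE 2.52 raw, 1.59 for change
- n = 189: SE 2.06 raw, 1.30 for change
- n = 252: SE 1.78 raw, 1.13 for change

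These treat patients as independent. SAP section 4 puts whole households in one arm, so the true SEs will differ somewhat.

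**4. Bias at Visit 2.** Arms are randomized, age is compared by arm in T16.1.9.4, and Visit 2 vital signs are taken before any removal for lice takes effect. Raw Visit 2 means are therefore less precise than they could be, but not biased by age.

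**5. Bias at Visits 3 and 4.** Protocol 10.6.7 says "Patients with live lice present at Visits 2 or 3 should be discontinued from the study", so the set of patients measured can change, and probably more on Placebo. With no product effect:

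Spurious arm difference = gap × (younger share among those retained on active − younger share among those retained on Placebo)

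- If exit is unrelated to age within each arm, the shares are unchanged and the difference is 0.
- If exit by Visit 4 were 28% younger and 22% older on active, and 85% and 75% on Placebo, with equal shares at entry, the younger shares would be 0.72/1.50 = 0.480 and 0.15/0.40 = 0.375. The difference of 0.105 times a gap of 20 to 50 is about 2 to 5 beats/min.

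The second case shows only what would follow if exit depended on age and patients who left supplied no Visit 4 value. Counting early-termination values as Visit 4 would largely remove the shift there; any Visit 3 shift would rest on the age condition.

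**The case against.** A reader might infer that age-related exit will make the products look different when they are not. The documents do not support that. Nothing says that clearing lice, and hence leaving, depends on age. Index patients are the youngest in the household and enter with at least 3 live lice rather than 1, but that does not show that they clear less often. Protocol 10.3.4, 10.8 and 12.2.4 call for End of Study procedures, or the Visit 4 form, at early termination, and vital signs are among those procedures. Listings L16.2.5 and L16.2.8.1 combine Visit 4 with discontinuation. If T16.1.9.15 does the same, the Visit 4 shift largely disappears, but that shell does not say. Protocol 10.5.2, read literally, brings treated household members back at Visit 2 only. On that reading Visits 3 and 4 hold index patients alone in every arm, and a shift from the index/non-index mix is zero.

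A reader might also turn the precision gain into power. With 126 per arm, SD 20 and correlation 0.8, a 5 beats/min shift would reach two-sided 5% with probability 51% on raw values and 88% on change. No such test is planned, and 126 counts index patients only. At 189 to 252 per arm the raw figure is about 68% to 80%. These percentages should not be cited as a property of the trial.

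Individual abnormalities have other routes to notice. Protocol 10.6.4 has significant changes reported as adverse events. L16.2.8.2 shows each patient's four visits in sequence, and age can be linked from L16.2.4.1 by patient number. The product is a single application rinsed off after 10 minutes, and the documents name no vital-sign harm.

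All of this stands. It limits the consequence, but none of it supplies a within-patient summary by arm.

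**Conclusion.** The gap is real and its impact is low. The planned table pools all ages and ignores the pre-dose value, so it is less sensitive to a post-dose change than the collected data allow. At Visit 2 the loss is in precision only. On assumed inputs the standard error of an arm difference would fall by about 37% at correlation 0.8, with a range of 11% to 55% for correlations of 0.6 to 0.9. The documents give no value for the correlation or the SD.

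A spurious difference at Visits 3 and 4 is a possibility and not a finding. It would need exit to depend on age, which the documents do not establish. For Visit 4 it would also need early-termination values to be left out of the Visit 4 rows, a mapping that T16.1.9.15 leaves unstated. This is a tabulation choice and not a question of clinical management.

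**What to change.** In SAP 8.3.3 and T16.1.9.15:

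- Add change from Visit 1 at each post-dose visit, for patients with both values, and show that n.
- Name the Visit 2 change as the main descriptive vital-sign comparison, since it is taken the day after dosing and before lice-related removal.
- Keep the raw-value summaries.
- State whether vital signs taken at early termination are tabulated as Visit 4.

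Add an age column to L16.2.8.2. A few broad age groups in the table are optional.

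Protocol 10.5.2 should be reconciled with the visit schematic and the Day 15 endpoint in index plus non-index patients, because it decides whose values the Visit 3 and 4 rows contain.

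The cost is a few lines of SAP text and two revised shells. All the data are already collected. The table becomes longer, and age groups, if used, would leave small cells among the youngest.
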